14.1 Study Medication Description (from Pfizer, Inc.)

Azithromycin

Zithromax® for oral suspension is supplied in bottles containing azithromycin dehydrate powder equivalent to 1200mg per bottle and the following inactive ingredients: sucrose; tribasic anhydrous sodium phosphate; hydroxypropyl cellulose; xanthan gum; FD&C Red #40; and flavoring including spray dried artificial cherry, crème de vanilla, and banana. After constitution, a 5mL suspension contains 200mg of azithromycin.

14.1 Dosage Information

Azithromycin and placebo will be administered as a single dose, in oral suspension form for children. Dosing will follow the WHO recommendations for treatment of active trachoma:

- Single dose of 20mg/kg in children (up to the maximum adult dose of 1g)
- Height-based dosing of children (this dosing method is supported by the WHO)

Individuals who are allergic to macrolides/azalides will not be treated.

14.2 Medication Procurement/Donation

Azithromycin (Zithromax®) and the placebo have been donated by the Pfizer Corporation. There will be no costs to acquiring the study medication. Pfizer, Inc. will ship azithromycin and placebo directly to the study sites.

Representatives of each study site will manage the customs process and transport the medication from the port to storage sites.

14.3 Medication Quality Control

Study medication will be stored at each country site prior to use. The study coordinator and other local staff will regularly check and record the study medication expiration dates. The expiration dates on the medication containers will be strictly monitored and all expired study medicine will be discarded appropriately.

14.4 Antibiotic Distribution & Monitoring Coverage

After the MORDOR 0 census and monitoring/collection is complete, treatment (azithromycin and placebo) will be administered to all eligible community members per study protocol. Teams will participate in training exercises regarding drug/placebo distribution and recording techniques prior to each treatment cycle. Training will be in accordance with the Zithromax Program Manager's Guide from the International Trachoma Initiative.

During mass drug administration, distribution team members will use tablet computers equipped with an electronic data capture system to seek out each eligible child on the census, administer antibiotic or placebo, and record whether or not each person has been treated. The distribution team will document individual reasons for not being treated (e.g. death, temporary absence, permanent migration, refusal of treatment, etc.). Consumption of medication will be directly observed and the dose distributed will be documented in the electronic data capture system.

We will estimate antibiotic coverage from the most recent biannual census records, aiming for treatment of 80% of children. At the end of each treatment round, the UCSF DCC will identify any children who have missed 2 or more consecutive treatments, and forward this information to the site study coordinator. Census teams will discern the reason for missing treatments (including unrecorded death) at the next scheduled census. This system will serve as a quality control mechanism to reduce the number of false negative deaths in the study.

14.5 Adverse Reactions/Side Effects

Azithromycin is generally well-tolerated. The most common side effects of azithromycin are diarrhea, nausea, abdominal pain, and vomiting, each of which may occur in fewer than one in twenty persons who receive azithromycin. Rarer side effects include abnormal liver function tests, allergic reactions, and nervousness. Diarrhea due to *Clostridium difficile* has been reported in rare cases.

During the consent process, the common adverse reactions that may occur will be explained to parents/guardians and they will be advised to communicate adverse events to local program representatives immediately. If, for any reason, the participant needs further care, they will be referred to the nearest health center for examination and treatment.

The trial sites will be masked to outcomes, so the responsibility for monitoring interim analysis will fall on the DSMC. Statistical monitoring is discussed in the Statistical Analysis Plan. The Data Safety and Monitoring Committee (DSMC) will be given authority to discontinue treatments at any time if there is evidence of unexpected harm.

14.6 Adverse Events Systems

Both active and passive monitoring systems for adverse events are in place for this study, and these monitoring activities will specifically include (but will not be limited to) treated 1-6 month olds. We will monitor adverse events following mass treatments actively at each follow-up census and during a house-to-house survey of all 1-6 month olds in a random selection of azithromycin and control communities.

14.6.1 Passive Adverse Events Monitoring

We will implement a passive monitoring system during the treatment phase, by instructing parents to report any adverse events in the two weeks following each mass azithromycin distribution to a local healthcare provider. Children will be referred for follow up care on a case-by-case basis.

14.6.2 Active Adverse Events Monitoring

During Census

We will employ two forms of active monitoring for adverse events. First, during each follow-up census we will ask the guardians of all 7-12 month-old children in all study communities (both mortality and morbidity), whether their children had an adverse event after the previous mass medication distribution. This will allow assessment of adverse events from medication distribution among the individuals aged 1-6 months at the time of the distribution. This information will be incorporated into the electronic data capture system so that this question is asked for any child aged 7-12 months. Note that this method will be subject to recall bias, so we will also perform a house-to-house survey (described below).

Infant Adverse Events Survey

To identify any adverse events associated with mass treatment, the UCSF DCC will randomly select 30 study communities (15 azithromycin and 15 control communities) to participate in an adverse events survey. This survey will be performed by the census workers masked to treatment arm, approximately 2 weeks after a mass medication distribution. During the survey, adverse events will be elicited only for study participants aged 1-6 months at the previous census. A structured questionnaire will be performed to elicit dangerous side effects, followed by an open-ended question. Specifically, we will ask the primary caregiver about the following symptoms during the time since the previous antibiotic distribution: abdominal pain, vomiting, nausea, diarrhea, dyspepsia, constipation, hemorrhoids or rash. To elicit symptoms of serious infantile hypertrophic pyloric stenosis which has been reported in rare occasions with macrolide use, census workers will be trained to ask about projectile vomiting and feeding problems.

Training

The household survey team will be the same individuals who conducted the census. They will be trained in survey administration methods, including:

- 1. Obtaining informed consent
- 2. Accurately selecting the appropriate households to interview
- 3. Remaining neutral when asking questions (i.e. asking the question exactly as it is written on the paper in a neutral tone of voice, so as not to lead the respondent or introduce bias)

Serious Adverse Events

Any serious adverse events (SAE) will be reported to Pfizer. An **IIR SAE Form** (*Investigator-Initiated Research Serious Adverse Events Form*) will be completed for each event. (See Appendix for form and complete instructions.)

According to Pfizer, an SAE is any adverse event that:

- Results in death
- Is life-threatening (i.e., causes an immediate risk of death)
- Requires inpatient hospitalization or prolongation of existing hospitalization
- Results in persistent or significant disability or incapacity
- Results in a congenital anomaly or birth defect

Or that is considered to be:

• An important medical event

All community residents will be advised to alert a village health worker if they experience, within one week of mass treatment, a serious adverse event (by the preceding definition). An SAE report must be submitted for all deaths in the study – regardless of the time of treatment. The local health worker will report to the on-site study coordinator; who must, within 24 hours, submit a Pfizer IIR SAE Form to [contact]. TL will review, and forward to Pfizer and/or the Medical Monitor, as appropriate. SAEs must be submitted to Pfizer within 24 hours of receipt from the on-site coordinator. TL will also forward SAE to DSMC if meets criteria of being possibly related to study drug.

Deaths that are reported to the study team outside of the biannual census (primary outcome) will be reported as an SAE to Pfizer. Note that deaths identified via the biannual census, which constitute the primary outcome, will not be reported as SAEs. Deaths that are reported to the study team as part of the biannual census will be reported to Pfizer in aggregate, not by arm, on a quarterly basis.

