The site study coordinator will supervise all census activities. Formal checks of census quality will be conducted through the random census verification. In addition, the study coordinator will visualize all censused households using imagery from GoogleMaps. The goal of this activity will be to minimize the chances of missing large neighborhoods or specific regions within study communities. The study coordinator will also check the data entry progress for each community, paying special attention at the follow-up censuses, as to whether there are any missing data for the "vital status" variable (i.e., present, dead, absent). Once the study coordinator is confident that the entire community has been reached, and that the amount of missing data are acceptable (defined as <10% of children in a community), the study coordinator (or other research team member) will certify the census data collection for that community complete via Salesforce. Changes can be made to the record at different time points, but these changes will not be reflected until the subsequent census. All changes are time and date stamped in the database.

Census Timing

The census will be performed prior to each mass azithromycin/placebo distribution. Study sites may choose to perform the census activities over a discrete time period (e.g., all communities completed over a 1-month period, requiring census activities to take place simultaneously in many communities at once) or alternatively in a "rolling" fashion (e.g., all communities completed over a 6-month period, requiring fewer census teams to be active at once). In either case, each community must be censused every 6 months, so it may not take more than 6 months to complete all communities. The census must be completed (i.e., "locked") at the household level before treatment can be given.

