9.1. Population

We will collect nasopharyngeal and stool samples on a random set of 40 children aged 1-60 months from each of the communities in the Morbidity study. Children will be selected from the current study census. The swabbing visits will occur after the census but **before** treatment. The randomized registration list of children will be provided to the site study coordinator before the swabbing visit. The Study Coordinator will give this list to the community for mobilization prior to examinations.

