14.6.3 Adverse Events Data

We will keep records and report all adverse events of azithromycin to the DSMC. We will report both efficacy and side effects of azithromycin separately for the 1-6 month old age group. For any "sudden deaths" believed to be associated with azithromycin treatment, key informants will immediately notify the verbal autopsy interviewer via SMS message or another appropriate form of rapid communication.

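### The census adverse-event question (Protocol 14.6.2) is triggered by current age, so it matches the intended 1-6 month dosed group only if the distribution-to-census gap is exactly six months

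*Protocol*

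**What the plan says.** Protocol 14.6.2 describes two active systems. In the first, at each follow-up census in all mortality and morbidity communities, guardians are asked "whether their children had an adverse event after the previous mass medication distribution". The tablet is set so that "this question is asked for any child aged 7-12 months". The purpose is stated as: "This will allow assessment of adverse events from medication distribution among the individuals aged 1-6 months at the time of the distribution". Section 14.6.3 then commits to a separate report: "We will report both efficacy and side effects of azithromycin separately for the 1-6 month old age group".

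On timing, Section 6.1 says "The census will be performed prior to each mass azithromycin/placebo distribution" and "each community must be censused every 6 months". SAP 2.1.1 describes later censuses as only roughly six months apart. For the first round, Section 14.4 adds a further step: "After the MORDOR 0 census and monitoring/collection is complete, treatment (azithromycin and placebo) will be administered". In morbidity communities, Section 9.1 places the swabbing visit between census and treatment.

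On who is dosed, Section 4.2 fixes eligibility by age at the census that opens each six-month segment. Section 5.1.1 and the opening of Chapter 14 refer to age on the current census. Section 5.1.1 also makes children eligible from the day they reach one month, without naming the date on which that is judged. Chapter 14 adds a minimum weight of 3.8 kg.

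**The concern.** The rule uses age at the census as a stand-in for two facts that are recorded elsewhere: age at the last distribution, and whether a dose was given. If the gap from dose to census differs from six months, the band of children asked slides against the band of children intended.

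A child wrongly included can be taken out later. A child never asked cannot be recovered, because the question refers only to the most recent distribution. This is the only active monitoring carried out in every community, and the protocol promises side-effect reporting for exactly this age group.

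**Working it through.** **Inputs.** Ages are read in completed months, so 1-6 is [1, 7) and 7-12 is [7, 13). Let *a* be age at one census, *I* the interval to the next census, *L* the lag from census to dose, and *g* = *I* − *L* the gap from dose to next census. The nominal *I* is 6 months (Section 6.1). The documents give neither *L* nor the spread of *I*. I assume *L* from 0 to 1 month, *I* from 5 to 7 months, and uniform ages.

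**The plan's own mapping.** The implied offset is 7 − 1 = 6 and 13 − 7 = 6 months. With *I* = 6 and *L* = 0 the bands coincide and nobody is missed.

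**Rules.** A child is asked if 7 ≤ *a* + *I* < 13. A dosed child is in the target group if 1 ≤ *a* + *L* < 7. There are two readings of eligibility:

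- Reading A, age judged at the census: dosed only if *a* ≥ 1.
- Reading B, age judged on the dosing day: dosed if *a* + *L* ≥ 1.

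**Shares.**

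- Youngest missed, reading A: (6 − *I*)/(6 − *L*) when *I* < 6, otherwise 0.
- Youngest missed, reading B: (6 − *g*)/6 when *g* < 6, otherwise 0.
- Oldest missed, with *L* = 0: (*I* − 6)/6 when *I* > 6.
- Of those asked, dosed at 7 months or older: (6 − *g*)/6 when *g* < 6.
- Of those asked, under 1 month at the distribution, with *L* = 0: (*I* − 6)/6 when *I* > 6.

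| *I* | *L* | *g* | Youngest missed, A | Youngest missed, B | Oldest missed | Asked, dosed at 7+ months | Asked, under 1 month at distribution |
|---|---|---|---|---|---|---|---|
| 6 | 0 | 6 | 0% | 0% | 0% | 0% | 0% |
| 5.5 | 0 | 5.5 | 8.3% | 8.3% | 0% | 8.3% | 0% |
| 5 | 0 | 5 | 16.7% | 16.7% | 0% | 16.7% | 0% |
| 5.5 | 0.5 | 5 | 9.1% | 16.7% | 0% | 16.7% | 0% |
| 6 | 0.5 | 5.5 | 0% | 8.3% | 0% | 8.3% | 0% |
| 6 | 1 | 5 | 0% | 16.7% | 0% | 16.7% | 0% |
| 6.5 | 0 | 6.5 | 0% | 0% | 8.3% | 0% | 8.3% |
| 7 | 0 | 7 | 0% | 0% | 16.7% | 0% | 16.7% |

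For example, *I* = 5 and *L* = 0 gives (6 − 5)/6 = 16.7%, and *I* = 5.5 with *L* = 0.5 under reading A gives 0.5/5.5 = 9.1%.

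**Why lag alone differs between the readings.** Take *I* = 6 and *L* = 0.5. Under reading A the youngest dosed child is 1.0 month at the census, 1.5 at dosing and 7.0 at the next census, and so is asked. Under reading B a child of 0.5 months at the census is dosed at 1.0 and is 6.5 at the next census, and so is not asked.

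**No second chance.** A child aged 6.5 months at one census is 12.5 months six months later and is then asked, but about the later distribution.

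**Undosed infants.** The trigger uses no dose record, so children under the weight floor, allergic, absent or refused are asked whatever the gap. Section 14.4 aims to treat 80% of children. If infants matched that aim, about 1 − 0.80 = 20% of those on the census would be undosed.

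**The case against.** A reader might infer that any gap under six months drops the youngest infants. The main eligibility text does not support that. Sections 4.2 and 5.1.1 and Chapter 14 mostly tie eligibility to age on the census, and then lag alone loses nobody while censuses are six months apart. Only the undated one-month sentence in Section 5.1.1 leaves the other reading open.

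The lag may also be short. Section 6.1 locks the census household by household before treatment, and Section 18.1 allows for treatment at the time of the census. The sampling step that lengthens the lag concerns only 30 communities per country (in Niger 30 of 646, or 4.6%). The weight floor removes some of the youngest infants from dosing, so uniform ages probably overstate the loss at that end. An interval well away from six months would go against Section 6.1. The plus-or-minus one month note in the Section 4.3 table is attached to the baseline window.

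A reader might also infer that the 1-6 month safety rate is necessarily diluted. The plan nowhere says that everyone asked will be counted as exposed. Section 14.6 speaks of treated infants, and Section 14.4 records treatment and dose for each child, so older or undosed children can be separated. However, Section 14.6 does not describe that linkage.

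Nor do the documents support saying that the check for pyloric stenosis fails. That probing belongs to the house-to-house survey, which is keyed to age at the previous census and runs about two weeks after distribution, so this drift does not touch it. The protocol itself notes recall bias in the census question and adds the survey for that reason. Passive and serious adverse-event reporting also continue.

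All of this stands, and it limits the size of the problem. It does not make the trigger meet its stated purpose. The survey covers only 30 communities, and unasked infants stay unasked.

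**Conclusion.** The concern holds in a limited form. A current-age trigger reproduces the intended group only at an exact six-month gap. With dosing at the census and uniform ages, intervals of 5.5 and 5 months miss about 8% and 17% of target infants at the young end, and intervals of 6.5 and 7 months miss the same shares at the old end. Whether a census-to-dose lag adds to the young-end loss depends on eligibility wording that the protocol does not settle. If age is judged at the census, the lag only brings in children dosed at 7 months or older.

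The percentages illustrate a mechanism and do not estimate what would happen in the field, since the documents give no distribution of lags, intervals or infant ages. The mortality outcome is not affected. The flaw lies in a secondary, recall-limited safety item, and it is worth correcting because the omissions are permanent and the data needed to avoid them are already collected.

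**What to change.** In Section 14.6.2, show the question for every child whose record has a dose given at age 1-6 months at the previous distribution, whatever the child's age at the census. In Section 14.6.3, define the 1-6 month safety group by recorded age at dosing and recorded dose. Among surviving, re-censused children with complete records, the share missed because of age then falls to 0% for every interval and lag.

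Separately, reconcile Sections 4.2, 5.1.1 and Chapter 14 on the date at which the one-month age is assessed. This review takes no position on which date it should be.

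The cost is a small change to the tablet application and a few sentences of text, with no added visits. The application manual is not among the documents, so the programming effort is a judgement. The downside is reliance on the treatment record: a dosed infant whose dose was not entered would not be asked.

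### The one-week alert for serious adverse events is shorter than the two-week window for any adverse event, so non-fatal serious events on days 8 to 14 have no explicit expedited path to the study

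*Protocol*

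**What the plan says.** The protocol gives families three reporting instructions.

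- Section 14.5, at consent: "they will be advised to communicate adverse events to local program representatives immediately". It sets no time limit and no threshold of seriousness.
- Section 14.6.1, passive monitoring: parents are to "report any adverse events in the two weeks following each mass azithromycin distribution to a local healthcare provider". The stated follow-up is referral for care, case by case.
- Section 14.6.2, serious adverse events: residents are to "alert a village health worker if they experience, within one week of mass treatment, a serious adverse event". The chain then continues: "The local health worker will report to the on-site study coordinator", and the coordinator has 24 hours to submit the form.

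Section 14.6.2 opens its serious-event text with a promise that has no time limit: "Any serious adverse events (SAE) will be reported to Pfizer". Deaths have their own rules there. One sentence says "An SAE report must be submitted for all deaths in the study", whatever the time since treatment. A later paragraph says that "deaths identified via the biannual census, which constitute the primary outcome, will not be reported as SAEs"; those deaths go to Pfizer in aggregate.

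The same section describes two active checks. One is a survey of infants aged 1-6 months in 30 communities: "This survey will be performed by the census workers masked to treatment arm, approximately 2 weeks after a mass medication distribution". The other is a question at each follow-up census, in all communities, to guardians of children who are then 7-12 months old. Section 14.6.3 adds that adverse events of azithromycin are recorded and reported to the Data and Safety Monitoring Committee (DSMC).

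**The concern.** The route that ends in an expedited SAE form has a shorter window than the protocol uses for adverse events in general. A child admitted to hospital on day 10 meets the SAE definition in 14.6.2 but falls outside the advice to alert the village health worker. Under 14.6.1 the parent is still asked to report the event, but to a healthcare provider who has no stated duty to inform the study. Under 14.5 the parent tells a program representative, again with no stated onward step.

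The three recipients are named differently and are never defined or equated. At stake is prompt safety information on non-fatal serious events after mass treatment of children from one month of age. The 24-hour form, review by the Medical Monitor and forwarding to the DSMC can act only on events that reach the coordinator.

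**Working it through.** The plan gives no figure to reproduce. The check sets the reporting channels side by side.

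| Protocol place | Events | Window | First recipient | Stated next step |
|---|---|---|---|---|
| 14.5 | Adverse events | None given | Local program representatives | Referral to a health center if care is needed |
| 14.6.1 | Any adverse event | 2 weeks (14 days) | Local healthcare provider | Referral for care |
| 14.6.2, serious events | Serious | 1 week (7 days) | Village health worker | Site coordinator, SAE form within 24 hours |
| 14.6.2, infant survey | Ages 1-6 months, 30 communities | Asked at about 2 weeks | Census workers | No step to the SAE form stated |
| 14.6.2, census question | Ages 7-12 months at census, all communities | Asked at the next census | Census workers | Entered in the data capture system; no step to the SAE form stated |

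**Difference in windows.** 14 − 7 = 7 days, that is, days 8 to 14. As a share of the two-week window, 7 / 14 = 50% of days. This is not a share of events. After day 14 neither timed instruction applies, so they do not conflict there.

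**Channels for a serious event on days 8 to 14:**

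1. *Death.* Covered: an SAE report whatever the time since treatment, or census capture with aggregate reporting.
2. *Non-fatal, child aged about 1-6 months at distribution, one of the 30 surveyed communities.* Asked about at roughly two weeks and again at the next census.
3. *Non-fatal, same age, any other community.* The only active capture is the census question. Censuses are six months apart, and 14.6.2 itself concedes recall bias for this method. It cannot serve a 24-hour report.
4. *Non-fatal, older child, any community.* Neither active check applies, because the survey is limited to ages 1-6 months even inside the 30 communities. What remains is 14.6.1 and 14.5, neither of which states a step to the coordinator.

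Group 4 is the main gap. Group 3 has capture, but late. The same holds at each distribution round.

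**The case against.** The case against is substantial, and much of it stands.

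- A reader might infer that serious events on days 8 to 14 have no route to the study at all. The documents do not support that. Section 14.6.1 covers any adverse event, serious ones included; 14.5 is untimed; deaths are covered at any time; and infants are asked about at the next census everywhere.
- A reader might infer that families are told not to report after one week. No section says so. The one-week phrase is advice to residents. It does not limit the study's untimed commitment to report any SAE, and the word *only* does not appear in it.
- A reader might infer that half of the serious events are lost, or that they are hidden from Pfizer and the DSMC. The 50% is a share of days. The documents give no timing of serious events and do not call two weeks a risk period. Section 14.6.3 commits to reporting adverse events of azithromycin to the DSMC. What can be said is that an onward step is not stated.
- The recipients may overlap in practice. Section 14.6.2 itself moves from a village health worker to a local health worker. The site appendices, the infant survey form and the SAE completion guide are listed but were not available, and consent pages were removed. A duty to pass events on could be written there.

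None of this removes the conflict in the main text. The commitment to report any SAE has no time limit, while the one instruction that explicitly feeds the SAE form is limited to a week. The commitment to the DSMC can be met only for events that reach the study.

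**Conclusion.** The point holds as a conflict between stated rules, limited to non-fatal SAEs on days 8 to 14. For these, no explicit expedited path leads to the coordinator and the SAE form. It applies mainly to children older than about 6 months at distribution, in all communities. For younger children outside the 30 surveyed communities, active capture exists but comes about six months later.

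The difference is 7 days in each round. The number or share of serious events affected cannot be estimated from the documents. The ascertainment of deaths for the primary outcome is not affected.

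The conclusion assumes that the local healthcare provider of 14.6.1 and the program representatives of 14.5 are not already bound, in an appendix or training document, to notify the coordinator. If they are, the remaining fault is the mismatch in windows and names. The change is worth making because it concerns safety reporting and costs little.

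**What to change.** Reconcile 14.5, 14.6.1 and 14.6.2, and the consent script, into one reporting instruction:

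1. Make the serious-event alert window no shorter than the protocol's own window for any adverse event.
2. Name the recipient once, define the role, and use the same term throughout.
3. State that any healthcare provider, program representative or survey worker who learns of an SAE passes it to the site coordinator by the existing 24-hour route.

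Before editing, check the site appendices and the SAE completion guide for definitions or duties that already do part of this, and bring them into the main text.

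The cost is wording in the protocol and consent script, a short addition to training, and a few more SAE forms per round. The design, the sample size and the primary analysis do not change.
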